5.6 OTHER ASSESSMENTS

For the purpose of a separate health economic analysis (such as cost-utility analysis), health care resource utilisation (HCRU) data will be collected throughout the trial. Resource use data collected for calculating direct costs will include unscheduled hospitalisations, healthcare provider visits, and emergency room/intensive care unit use. Non-medical resource use data will include changes in work productivity.

The economic evaluation of the HCRU data will not be part of the clinical trial report but reported separately.

5.7 APPROPRIATENESS OF MEASUREMENTS

The measures conducted for primary, key secondary and secondary endpoints are using standard methods. Measures conducted for exploratory further endpoints might be new methodologies already used in clinical trials in SSc but not yet validated for this rare disease.

6. INVESTIGATIONAL PLAN

6.1 VISIT SCHEDULE

There is one screening visit (which may be preceded by a separate informed consent visit) and up to 11 visits planned within the 100 weeks treatment period (52 weeks until primary endpoint and additional 48 weeks on treatment), plus intermediate blood analyses and one follow-up Visit. The trial will last until:

- Follow-up visit of the last randomized patient if he/she completed 52 weeks of treatment, or
- Visit 9 of the last randomized patient if he/she discontinued treatment early but agreed to come to future visits as planned, or
- Follow-up visit of the last randomized patient if he/she discontinued treatment prematurely and did not agree to come to future visits

Approximately at this timepoint all ongoing patients will have their last trial visits and trial completion (patients on treatment will have an EOT and follow-up visit; patients who discontinue treatment early will have their next scheduled visit immediately).

After giving his/her informed consent, the patient will be screened for inclusion and exclusion criteria for the trial at Visit 1.

Visit 2 can be performed once the results from central laboratory of Visit 1 and central HRCT review are obtained. If for any reason the screening phase for an individual patient lasts for more than 6 weeks, then the laboratory examination for Visit 1 has to be repeated before randomization. The screening phase should not be longer than 12 weeks.

Rescreening is possible, rescreened patients will be assigned a new patient number.

The patient will be randomised at Visit 2 if all inclusion and none of the exclusion criteria are fulfilled.

The results of laboratory parameters from Visit 2 will become available only after Visit 2. Therefore, laboratory results from Visit 2 cannot qualify as exclusion criteria; laboratory results from Visit 1 will be used instead. In case laboratory results of Visit 2 would retrospectively fulfill an exclusion criterion, the patient should not continue receiving trial medication unless continuation is justified in writing by the Investigator.

Visits 2, 3, 4 and 5 will occur every 2 weeks. Visit 6 will be scheduled 6 weeks later, Visits 7 and 8 are planned every 12 weeks and further Visits (9, 10, 11 and 12/EOT) are planned every 16 weeks. Visits 6a, 7a, 8a, 9a, 10a and 11a (a-Visits) are intermediate laboratory control visits.

The samples for the 'a-Visits' may be drawn locally (i.e. local general practitioner [GP]). The Investigator would in that case give the required documentation to the patient, with the

Page 67 of 126

Proprietary confidential information © 2018 Boehringer Ingelheim International GmbH or one or more of its affiliated companies

corresponding trial kit for the respective 'a-Visit' to be sent to the central lab even if not at the trial site. Information, agreement and training of the respective local GP for blood draw will be ensured on an individual site basis consulting the sponsor's local monitor.

Pregnancy test will be performed in women of childbearing potential every 4-6 weeks. Urine dipstick test will be done at every visit and will be provided for at home pregnancy testing as soon as visit intervals are > 6 weeks (2 to 3 pregnancy test dipsticks to take home. Women of childbearing potential will be instructed accordingly.

The primary endpoint Visit 9 is scheduled 52 weeks after randomization, occurring 16 weeks after Visit 8. Visit 10, 11 and 12/EOT are scheduled every 16 weeks from Visit 9.

A window of ± 3 days for the Visits 3 to 6, ± 7 days for Visits 6a to 12 is allowed to accommodate scheduling problems. If a delay is observed for a particular visit, the original calendar schedule should be kept for subsequent visits (delays should not accumulate).

If treatment is discontinued, regardless if prematurely, after 100 weeks, or at the global end of the trial, an end of treatment visit (EOT) will be performed.

A follow-up visit has to be organized 28 days (+ 7 days) after the end of treatment visit.

Patients who have been treated until the predefined end of the trial will have the possibility to participate in an extension trial to receive nintedanib open label.

Page 68 of 126

Proprietary confidential information © 2018 Boehringer Ingelheim International GmbH or one or more of its affiliated companies

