3. DESCRIPTION OF DESIGN AND TRIAL POPULATION

3.1 OVERALL TRIAL DESIGN AND PLAN

This is a multi-centre, multi-national, prospective, randomised, placebo-controlled, double blind clinical trial to investigate the efficacy and safety of nintedanib at a dose of 150 mg bid, in patients with SSc-ILD.

The main efficacy analysis will be assessed at week 52. Patients will stay on treatment up to a maximum of 100 weeks in order to collect follow-up safety and efficacy information (Figure 3.1: 1).

Patients on treatment will have their end of treatment visit (EOT visit) at the same time or before the planned Visit 9 of the last randomised patient. The EOT visit will replace either Visit 9, 10, 11 or 12, whatever is the latest possible visit before or at the planned visit 9 of the last randomised patient. For these patients, the trial ends with the completion of the follow-up visit 28 days after the EOT. All patients who have concluded the trial on treatment will be offered the opportunity to enter an open label extension trial.

Patients, who discontinued treatment but agreed to come to further visits, the last visit will be either Visit 9, 10, 11 or 12, whatever is the latest possible visit before or at the planned visit 9 of the last patient randomized. A follow up visit is not needed for patients who discontinued trial drug earlier.

After signing informed consent (IC) before or at Visit 1, a HRCT will be collected and sent for central eligibility review.

The initial screening Visit (Visit 1) will be performed and patients will enter a screening period of maximum 12 weeks. For detailed procedural assessments of patient's eligibility, and refer to the Flowchart and Section 6.2.1.

After receiving the HRCT central review eligibility result, Visit 2 will be scheduled and collection of clinical and safety laboratory, review of all In- and Exclusion Criteria and randomization will be performed by phone or Internet, using an Interactive phone/web Response System (IRT).

Patients with confirmed SSc-ILD diagnosis will be randomised to either nintedanib or placebo in a 1:1 stratified randomization and in addition stratified by ATA status (positive or negative).

Concomitant treatment rules, dose reduction procedures and short term drug interruptions in case of adverse events are described in Section 4.2.

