8.5 STATEMENT OF CONFIDENTIALITY

Individual patient medical information obtained as a result of this trial is considered confidential and disclosure to third parties is prohibited with the exceptions noted below. Patient confidentiality will be ensured by using patient identification code numbers.

Treatment data may be given to the patient's personal physician or to other appropriate medical personnel responsible for the patient's welfare. Data generated as a result of the trial need to be available for inspection on request by the participating physicians, the Sponsor's representatives, by the IRB / IEC and the regulatory authorities.

8.6 **END OF TRIAL**

The end of the trial is defined as last patient out.

For EU member states.

The IEC / competent authority in each participating EU member state needs to be notified about the end of the trial or early termination of the trial.

c03014699-05 Page 90 of 126 **Trial Protocol**

Proprietary confidential information © 2018 Boehringer Ingelheim International GmbH or one or more of its affiliated companies

For Japan:

When the trial is completed, the Investigator should inform the head of the trial site of the completion in writing, and the head of the trial site should promptly inform the IRB and Sponsor of the completion in writing.

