6.7 BASELINE, TIME WINDOWS AND CALCULATED VISITS

As a general rule, the last assessment/measurement before the date of first trial drug intake (included) will be used as baseline (possibly last screening assessment if no further available value).

Endpoints which are censored at Week 52 will be cut on Day 373 which is calculated as: Date of first trial drug intake (i.e. Day 1) + 372 (=365+7 day window per the CTP flow chart). All references to Day 373 throughout this document refer to this date which is 372 days after the date of first trial drug intake.

Visit windowing will be performed as described in [Tables 6.7: 1](#), [6.7: 2](#) and [6.7: 3](#), in order to assign data to the relevant study visit based on the actual day of the assessment. Data will be analysed using the re-calculated visits in the statistical tables. However, in the listings, all

visits performed will be displayed (even if outside time-window), along with the re-calculated visit.

Table 6.7: 1 Time windowing rules for spirometry, physical exam, vital signs, HCRU, mRSS, Digital ulcer, menstruation calendar

Time window of actual day ^[1]			Allocated to		
Start day	End day (included)	Length of the time-window [days]	Visit number	Visit name	Planned day of the visit
Last assessment before the date of first trial drug intake	1	1	1 or 2 ^[2]	Baseline	1
2	22	21	3	2 weeks	15
23	36	14	4	4 weeks	29
37	64	28	5	6 weeks	43
65	127	63	6	12 weeks	85

Table 6.7: 1 Time windowing rules for spirometry, physical exam, vital signs, HCRU, mRSS, Digital ulcer, menstruation calendar (cont'd)

Time window of actual day ^[1]			Allocated to		
128	211	84	7	24 weeks	169
212	309	98	8	36 weeks	253
310	373	63	9	52 weeks	365
374	533	161	10	68 weeks	477
534	645	112	11	84 weeks	589
646	708	63	12	100 weeks	701
709	Last trial drug intake + 27 ^[3]	Variable	NA	Between 100 weeks and follow-up visit	NA
Last trial drug intake + 28	Last trial drug intake + 35 ^[3]	7	FU	Follow-up	NA

Note: mRSS and Digital ulcer not measured at visits 3, 4, 5 and follow-up

[1] First trial drug intake date is taken into account as a reference to calculate time windows

[2] Depending on the last assessment before first trial drug intake (included), refer to [Section 6.7](#) for baseline definition

[3] These two periods only exist if follow-up visit occurs after 709 days (included)

Table 6.7: 2 Time windowing rules for SGRQ, FACIT-dyspnoea, SHAQ, EQ-5D-5L, patient global VAS, DLCO, SpO2, antoantibody assessment, Physician global VAS

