If after windowing of visits at baseline, two values fall within the same baseline interval, then the last value will be taken into account. If after windowing of post-baseline visits, two visits fall in the same interval, then the measurement closest to the planned visit will be taken into account. In case two measurements are equidistant from the planned visit, then the last one will be picked.

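### Protocol Section 6.1 gives an end-of-trial rule that conflicts with Section 3.1 and, in one branch, has no 52-week minimum (wrong as written, minor)

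*Protocol*

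**What the plan says.** Protocol Section 3.1 sets the last visit from a calendar date. Patients on drug have their end-of-treatment (EOT) visit "at the same time or before the planned Visit 9 of the last randomised patient". It replaces Visit 9, 10, 11 or 12, "whatever is the latest possible visit before or at the planned visit 9 of the last randomised patient". Patients off drug who still attend follow the same rule. Visit 9 is scheduled 52 weeks after randomisation (Section 6.1).

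The list in Protocol Section 6.1 depends on what the last randomised patient actually does:
- completes 52 weeks of treatment: that patient's follow-up visit;
- stops drug but keeps attending: "Visit 9 of the last randomized patient if he/she discontinued treatment early but agreed to come to future visits as planned";
- stops drug and refuses visits: "Follow-up visit of the last randomized patient if he/she discontinued treatment prematurely and did not agree to come to future visits".

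It continues: "Approximately at this timepoint all ongoing patients will have their last trial visits and trial completion". In brackets, it gives patients on drug an EOT and a follow-up visit, and gives patients who stopped drug early their next scheduled visit at once.

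Section 8.6 says only: "The end of the trial is defined as last patient out".

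**The concern.** The first two branches of Section 6.1 cannot end the trial before the last randomised patient's week 52. The third can. Follow-up is 28 (+7) days after EOT, so a last patient who stops drug at week w and refuses visits triggers closure at about week w + 4. Anyone randomised fewer than 52 - (w + 4) weeks before that patient would not reach Visit 9, the timepoint of the primary and both key secondary endpoints. Section 8.6 names no week, so it does not settle the matter.

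The sections also differ when nothing unusual happens. Section 3.1 gives an off-drug patient the latest scheduled visit at or before the planned date; Section 6.1 pulls the next visit forward. In that ordinary case every other patient is already past week 52, so only later data are affected. Sites still hold two closing instructions.

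**Working it through.** **1. Text.** The two anchors side by side:

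| Last randomised patient | Section 3.1 anchor | Section 6.1 anchor |
|---|---|---|
| Completes 52 weeks on drug | planned Visit 9, week 52 | follow-up visit, about week 56 |
| Stops drug, keeps attending | planned Visit 9, week 52 | Visit 9, week 52 |
| Stops drug at week w, refuses visits | planned Visit 9, week 52 | about week w + 4 |

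The third row falls short of week 52 whenever w is below about 48.

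**2. The plan's own figures.** Section 7.7 gives 260 per group, 70 mL, SD 245 mL and 90% power. Check: 70 / (245 × √(2/260)) = 3.26, and Φ(3.26 - 1.96) = 0.903. For mRSS, 2.6 points with SD 9 gives 0.909. For SGRQ, 3.7 points with SD 13 gives 0.901. All three agree with Section 7.7.

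**3. Patients stopped before Visit 9.** Assumed: 520 patients, uniform accrual over R = 78 weeks (Section 3.3 expects about 18 months), no other dropout. Count = 520 × (48 - w) / R.

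| w | Count at R = 78 |
|---|---|
| 12 | 520 × 36/78 = 240 |
| 24 | 520 × 24/78 = 160 |
| 36 | 520 × 12/78 = 80 |
| 48 | 0 |

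At w = 12 the count is 312 for R = 60 and 187 for R = 100. Under Section 3.1 it is 0 in every case.

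**4. No value in the SAP week-52 window (w = 12, R = 78).** SAP Section 6.7 uses days 310-373 for FVC and mRSS, and days 254-373 for SGRQ. EOT falls no earlier than week 16. Only FVC is repeated at the 28-day follow-up; for mRSS the SAP states "mRSS and Digital ulcer not measured at visits 3, 4, 5 and follow-up", and the flowchart schedules no questionnaires there.
- FVC: 520 × (309/7 - 4 - 16) / 78 = 161
- mRSS: 520 × (309/7 - 16) / 78 = 188
- SGRQ: 520 × (253/7 - 16) / 78 = 134

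**5. Primary slope (w = 12, R = 78).** SAP Sections 5 and 7.4.1 use follow-up FVC before week 52. SAP Section 6.7 keeps one value per window: if "two visits fall in the same interval, then the measurement closest to the planned visit will be taken into account". The calculation follows both rules. Assumed slope SD is 200 mL/yr and residual SD 100 mL, which match the protocol's SD: √(200² + 2 × 100²) = 245. Each patient's information is X′V⁻¹X, with X = [1, t] and V = XGX′ + σ²I. It is averaged over patients and multiplied by 260; the slope-difference variance is twice the slope element of the inverse. Power is Φ(70/SE - 1.96).

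| Baseline FVC | Full SE (mL/yr) | SE after closure | Increase | Power |
|---|---|---|---|---|
| among the responses (Protocol 7.3.1) | 19.8 | 21.1 | 6.4% | 94% to 91% |
| covariate only (SAP 7.4.1) | 20.1 | 21.6 | about 7% | 93.5% to 90.0% |

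**6. Key secondary endpoints (w = 12, R = 78).** MMRM information with compound symmetry and assumed correlation 0.5 to 0.8; EOT values go to their SAP window.
- mRSS, 2.6 points: SE up 8% to 17%, power 91% to about 80-87%
- SGRQ, 3.7 points: SE up 6% to 12%, power 90% to about 82-86%

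At w = 24 the SE increases are 3% to 8% for mRSS and 2% to 4% for SGRQ.

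**The case against.** The strongest reply is that the intent is not in doubt. Section 3.1 is the design section, the title promises at least 52 weeks, the synopsis puts the primary endpoint at 52 weeks, and Section 6.1 itself schedules Visit 9 at week 52. That stands. The trigger is also narrow: one particular patient must stop drug before about week 48 and refuse visits, and the sponsor must then follow Section 6.1 over Section 3.1. That stands too.

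A reader might infer that the primary test is under threat, since nearly half the patients could be cut short. A t-test restricted to the 140 per group who reach Visit 9 would indeed have only 67% power. The documents do not support that inference. The primary model is a random-slope analysis of all available FVC up to week 52, including EOT and follow-up values, so shortened patients still contribute.

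A reader might also take the amendment description, which lists Section 6.1 as clarified, as proof of a failed update. A difference between that log and the current text is not an error, and the point does not rest on it.

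What the reply does not remove is that Section 6.1 is an operative closing instruction and no other section says which rule prevails.

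**Conclusion.** Wrong as written, minor. Two current sections give different end-of-trial rules, and the third branch of Section 6.1 has no 52-week minimum. The practical risk is low. The documents do not support reading this as a design that allows less than 52 weeks, or as a flaw in the sample size.

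The patient counts rest on assumed uniform accrual, and the precision losses also on assumed variances and correlations, so they show scale only. In the week-12 illustration the primary test keeps about its planned 90% power. The key secondary tests bear more of the loss because neither mRSS nor SGRQ is measured at follow-up.

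**What to change.** In Protocol Section 6.1, replace the three bullets and the sentence after them, including its bracketed instruction, with the Section 3.1 rule:
- The trial lasts at least until the planned Visit 9 date of the last randomised patient (52 weeks after the last randomisation), whether or not that patient is still in the trial.
- Each patient's last visit is the latest of Visits 9 to 12 at or before that date. It is an EOT visit for patients on drug.
- Patients who were on drug have a follow-up visit 28 days after EOT.

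The cost is one paragraph of protocol wording and a notice to sites. The SAP and the sample size stay as they are.

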3.3.3 Exclusion criteria

Laboratory parameter thresholds (Visit 1)

- 1. AST, ALT > 1.5 x ULN.
- 2. Bilirubin >1.5 x ULN.
- 3. Creatinine clearance <30 mL/min calculated by Cockcroft–Gault formula (Appendix 10.2).

Laboratory parameters from Visit 1 have to satisfy the laboratory threshold values as shown above. Visit 2 laboratory results will be available only after randomization. In case at Visit 2 the results do no longer satisfy the entry criteria, the Investigator has to decide whether it is justified that the patient remains in the trial. The justification for decision needs to be documented. Laboratory parameters that are found to be abnormal at Visit 1 are allowed to be re-tested (once) if it is thought to be a measurement error (i.e. there was no abnormal result of this test in the recent history of the patient and there is no related clinical sign) or the result of a temporary and reversible medical condition, once that condition is resolved.

Proprietary confidential information © 2018 Boehringer Ingelheim International GmbH or one or more of its affiliated companies

Lung diseases

c03014699-05

- 4. Airway obstruction (pre-bronchodilator $FEV_1/FVC < 0.7$) at Visit 2.
- 5. In the opinion of the Investigator, other clinically significant pulmonary abnormalities.

Other diseases

- 6. Significant PH defined by any of the following:
 - a. Previous clinical or echocardiographic evidence of significant right heart failure
 - b. History of right heart catheterisation showing a cardiac index $\leq 2 \text{ l/min/m}^2$
 - c. PH requiring parenteral therapy with epoprostenol/treprostinil
- 7. Cardiovascular diseases, any of the following
 - a. Severe hypertension, uncontrolled under treatment (≥160/100 mmHg), within 6 month of Visit 1
 - b. Myocardial infarction within 6 months of Visit 1
 - c. Unstable cardiac angina within 6 months of Visit 1
- 8. More than 3 digital fingertip ulcers at Visit 2 or a history of severe digital necrosis requiring hospitalization or severe other ulcers at discretion of the investigator.
- 9. Bleeding risk, any of the following
 - a. Known genetic predisposition to bleeding.
 - b. Patients who require
 - i. Fibrinolysis, full-dose therapeutic anticoagulation (e.g. vitamin K antagonists, direct thrombin inhibitors, heparin, hirudin)
 - ii. High dose antiplatelet therapy.

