3.3.4 Removal of patients from therapy or assessments

3.3.4.1 Removal of individual patients from therapy

The trial medication has to be permanently discontinued in the following circumstances

- The patient experiences signs of hepatic injury, defined in Section 5.3.7.1.
- In the opinion of the investigator, the patient experiences unacceptable adverse events despite dose adjustments and supportive care.
- Use of concomitant treatment: as defined in Section 4.2.2 "restrictions".
- Parenteral feeding requirement.
- Pregnancy (refer to Section 5.3.6).
- If a patient becomes pregnant during the trial the investigational product needs to be stopped and the patient should be followed up until birth or otherwise termination of the pregnancy. The data of the patient will be collected and reported in the clinical trial report (CTR) until patient's last visit and any events thereafter will be reported in the BI drug safety database. Refer to Section 5.3.6 for detailed information on event reporting in case of pregnancy.

In the following cases discontinuation of trial medication is highly recommended. Only in special circumstances, the Investigator, upon thorough assessment of all available clinical data and taking into consideration the potential risks associated with administration of nintedanib, may decide not to withdraw the trial medication, even though one or more of the below mentioned criteria are fulfilled. In such a case, continuation of treatment with trial

Page 34 of 126

Proprietary confidential information © 2018 Boehringer Ingelheim International GmbH or one or more of its affiliated companies

medication should be discussed with the patient, and the decision and reasoning documented in the source data.

- Major surgery, including any abdominal or intestinal surgery.
- Anti-coagulation. Patients who require full-dose therapeutic anticoagulation (e.g. vitamin K antagonists, heparin, hirudin, direct thrombin inhibitors, etc), or high-dose antiplatelet therapy. (Prophylactic low dose heparin or heparin flush as needed for maintenance of an indwelling intravenous device (e.g. enoxaparin 4000 I.U. s.c. per day), as well as prophylactic use of antiplatelet therapy (e.g. acetyl salicylic acid up to 325 mg/day, or clopidogrel at 75 mg/day, or equivalent doses of other antiplatelet therapy is allowed.).
- Major thrombo-embolic events e.g. stroke, deep vein thrombosis, pulmonary embolism, myocardial infarction.

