4.2.1.2 Management of liver enzyme elevation

Evaluate the concomitant use of other drugs known to cause liver enzyme elevations. For a detailed guidance on how to manage liver enzyme elevations, please refer to Table 4.2.1.2: 1.

Table 4.2.1.2: 1: Recommendations for managing liver enzyme elevations

	AST or ALT increase to			Signs of hepatic injury*
	>1.5x to <3x ULN	≥3x to <5x ULN and no signs of hepatic injury (Section 5.3.6)	≥5x to <8x ULN and no signs of hepatic injury (Section 5.3.6)	(Section 5.3.6)
Visit 2 (randomization)	Withdraw trial medication or justify continuation ¹	Withdraw trial medication	Withdraw trial medication	Withdraw trial medication
Any other Visit	Continue as planned ²	Reduce dose or interrupt trial medication ³	Interrupt trial medication	Withdraw trial medication CLINICAL
		Close observation ⁴	Close observation ⁴	EVALUATION OF HEPATIC-INJURY (Section 5.3.6)
		After 2 weeks or any time later	After 2 weeks or any time later	
	<3x ULN	≥3x ULN	<3x ULN	>3x ULN
	Reduced: return to initial dose.	Permanently discontinue trial medication	Restart at reduced dose	Permanently discontinue trial medication.
	Interrupted: restart at reduced dose. Monitor bi- weekly for at least 8 weeks	Close observation ⁴	Monitor weekly for 4 weeks, then bi-weekly for at least 8 weeks	Close observation ⁴

Footnotes:

*Signs of hepatic injury are defined as

- ALT and/or AST ≥8 fold ULN
- ALT and/or AST ≥3 fold ULN and total bilirubin ≥2 fold ULN
- ALT and/or AST ≥3 fold ULN and unexplained INR >1,5
- ALT and/or AST ≥3 fold ULN and unexplained eosinophilia (>5%)
- ALT and/or AST ≥3 fold ULN and appearance of fatigue, nausea, vomiting, right upper abdominal quadrant pain or tenderness, fever and/or rash

phosphatase, total bilirubin, and eosinophils within 48 to 72 hours, then approximately 7 days, then approximately 2 weeks by using intermediate visit lab kit.

¹ Investigator to confirm in writing that continuation is justified (e.g. intermittent fluctuation of transaminases).

² According to visit schedule. Consider additional control visits as adequate.

³ To be decided by Investigator, based on individual risk assessment.

⁴Close observation: Re-test ALT and AST, alkaline

Page 43 of 126

Proprietary confidential information © 2018 Boehringer Ingelheim International GmbH or one or more of its affiliated companies

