5.3.3 Safety laboratory parameters

The laboratory tests at regular site visits will include:

Category Laboratory test	
Haematology Red blood cell count (RBC)	
Haemoglobin (Hb)	
Haematocrit (Hct)	
Mean corpuscular volume	
White blood cell count including differential	
Platelet count	
Biochemistry Aspartate aminotransferase (AST)	
Alanine transaminase (ALT)	
Gamma-glutamyl transferase (GGT)	
Alkaline phosphatase (ALK)	
Creatine kinase (CK)	
Lactate dehydrogenase (LDH)	
Total protein	
Total bilirubin	
Brain natriuretic peptide (BNP, only at V2, 7, 9,V12/EOT)	
Creatinine	
Glucose (non fasting)	
Uric acid	
Thyroid stimulating hormone (only at V2, 7, 9, V12/EOT)	
β-HCG (at Visit 2 only)	
Electrolytes Sodium	
Potassium	
Calcium	
Chloride	
Inorganic phosphorus	
Coagulation International normalized ratio (INR)	
Partial thromboplastin time (PTT)	
Prothrombin time (PT)	
Urinalysis pH, glucose, erythrocytes, leukocytes, protein, nitrite (semiquantitative	
measurements; -, +, ++, +++)	
Local Urine dipstick pregnancy test in all women of childbearing potential. If urine test is not	
acceptable to local authorities, a blood test must be done at a local laboratory.	

Trial Protocol

c03014699-05 Page 56 of 126 Proprietary confidential information © 2018 Boehringer Ingelheim International GmbH or one or more of its affiliated companies

The laboratory tests at intermediate 'a' visits will include:

Category	Laboratory test	
Biochemistry	Total protein, creatinine, electrolytes and liver function (AST, ALT, GGT, alkaline phosphatase, and total bilirubin)	
Urinalysis pH, glucose, erythrocytes, leukocytes, protein, nitrite (semiquantitative measurements; -, +, ++, +++)		
Local Urine dipstick pregnancy test in all women of childbearing potential. If urine test is not acceptable to local authorities, a blood test must be done at a local laboratory.		

Overall about 230 mL blood will be taken for standard safety laboratory during the course of the trial.

Creatinine clearance will be calculated based on serum creatinine according to Cockcroft and Gault (R96-0690, Appendix 10.2).

If laboratory values indicate abnormality, adequate and more frequent blood sampling may be performed at the discretion of the Investigator.

In case of liver function value elevations, close monitoring must be ensured by the Investigator. Refer to Section 4.2.1.2 for monitoring elevations and Section 3.3.4 for withdrawal criteria.

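### For AST/ALT of ≥3x to <8x ULN at Visit 2 without signs of hepatic injury, Protocol 6.1 permits justified continuation, Table 4.2.1.2:1 says withdraw, and nothing says which prevails

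*Protocol*

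**What the plan says.** Eligibility on liver enzymes is judged on the Visit 1 sample: Protocol 3.3.3, criterion 1, excludes AST or ALT above 1.5x ULN. A second sample is taken at Visit 2, but its results come back after randomisation. Several places in the protocol bear on what happens next.

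- **Section 6.1** covers any Visit 2 result that would have met an exclusion criterion: "the patient should not continue receiving trial medication unless continuation is justified in writing by the Investigator". The default is to stop. The exception has no upper limit.
- **Table 4.2.1.2:1, Visit 2 row**, is graded by AST/ALT level. At >1.5x to <3x ULN it reads "Withdraw trial medication or justify continuation", with footnote 1 adding "Investigator to confirm in writing that continuation is justified". At ≥3x to <5x, at ≥5x to <8x, and for signs of hepatic injury, the instruction is withdrawal alone, without the footnote.
- **Section 3.3.4.1** lists the mandatory stopping rules: "The trial medication has to be permanently discontinued in the following circumstances". The hepatic entry is "The patient experiences signs of hepatic injury, defined in Section 5.3.7.1". That definition takes in ≥8x ULN, or ≥3x ULN together with a further laboratory or clinical sign. An isolated value of ≥3x to <8x does not meet it.
- **Section 5.3.3** directs sites as follows: "Refer to Section 4.2.1.2 for monitoring elevations and Section 3.3.4 for withdrawal criteria".
- **Section 3.3.3** has its own sentence on Visit 2 results: "the Investigator has to decide whether it is justified that the patient remains in the trial", with the reason documented.

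**The concern.** Sections 6.1 and 4.2.1.2 use the same device, written justification by the investigator, but only the table gives it a ceiling. Between 3x and 8x ULN a site can therefore follow 6.1 to the letter and still act against the table. Trial medication is dispensed at Visit 2, before the result is known, so the rule applies to patients who may already be taking the drug.

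What is at stake is patient safety and uniform handling across sites. Section 2.3 reports drug-induced liver injury with nintedanib, including fatal cases. The exception in 6.1 requires neither dose reduction nor interruption. Read alone, it would allow full-dose continuation at a level where the table calls for reduction or interruption at every later visit.

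**Working it through.** No statistical formula applies. The check sets the rules side by side by AST/ALT level at Visit 2.

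| AST/ALT at Visit 2 | Section 6.1 | Table, Visit 2 row | Table, any other visit | Mandatory stop in 3.3.4.1? | Result |
|---|---|---|---|---|---|
| >1.5x to <3x ULN | Stop unless justified in writing | Withdraw or justify in writing | Continue | No | Agree |
| ≥3x to <5x, no signs of hepatic injury | Stop unless justified in writing | Withdraw | Reduce or interrupt | No | Conflict |
| ≥5x to <8x, no signs of hepatic injury | Stop unless justified in writing | Withdraw | Interrupt | No | Conflict |
| Signs of hepatic injury (includes ≥8x) | Stop unless justified in writing | Withdraw | Withdraw | Yes | Settled by 3.3.4.1 |

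Of the four cells in the Visit 2 row, one agrees with 6.1, two conflict with it, and one is settled elsewhere (1 + 2 + 1 = 4).

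**Does anything rank the two texts?** Section 6.1 does not mention the table, and 4.2.1.2 does not mention 6.1. The table is introduced as guidance and titled as recommendations. Section 5.3.3 sends sites to 4.2.1.2 for monitoring and to 3.3.4 for withdrawal, and 3.3.4.1 has no entry for an isolated value in this band. A site that follows the cross-references finds an instruction to withdraw only in the table.

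**How far must a value move?** An eligible patient has at most 1.5x ULN at Visit 1.

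- To enter the band: 3.0 / 1.5 = 2.0-fold rise from the Visit 1 limit.
- To reach its upper bound: 8.0 / 1.5 = 5.3-fold rise.

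A patient starting lower needs a larger rise. The Visit 1 laboratory is repeated if screening lasts more than 6 weeks, which shortens the gap between the two samples. The documents give no frequency for such rises.

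**How long could full dosing continue?** The flowchart puts the next safety laboratory at Visit 3, day 15 ±3, so between day 12 and day 18. That is 11 to 17 days after Day 1 (12 − 1 and 18 − 1). From then on the table's row for other visits applies, and nothing disputes it: reduce or interrupt at ≥3x to <5x, interrupt at ≥5x to <8x, with close observation in both. A value still at or above 3x after two weeks of that handling leads to permanent discontinuation.

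**The case against.** The best reply is that both texts can be obeyed. Section 6.1 is a general rule for every laboratory exclusion criterion, including bilirubin, creatinine clearance and coagulation. The table is specific to AST/ALT and has a row for this very visit. Withdrawing satisfies both, nothing in 6.1 compels continuation, and a specific rule normally displaces a general one. On this view all that is missing is a cross-reference.

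Much of this stands. Reading the table as the governing rule is reasonable and probably what was intended. But the protocol does not say so, and 6.1 is the text written for Visit 2 results that arrive after randomisation. A site that continues with written justification complies with 6.1 and departs from the table.

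The safeguards also stand. Section 6.1 defaults to stopping. Section 2.3 requires reduction or interruption for hepatic toxicity and no further dosing until the abnormal values have recovered, although it does not name Visit 2 or require withdrawal. Section 5.3.3 adds "In case of liver function value elevations, close monitoring must be ensured by the Investigator". The Visit 3 laboratory brings a persistent elevation under an undisputed rule.

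A reader might infer two further things that the documents do not support.

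- *That 3.3.3 is a second rule permitting continued dosing.* It speaks of remaining in the trial. The protocol separates that from staying on drug: patients who stop medication are asked to keep to their visit schedule. A patient can be withdrawn from drug under the table and still remain in the trial under 3.3.3, so that section is supporting context only.
- *That the conflict carries into the SAP's important protocol violations (Table 6.2:1).* Code A2.1 uses Visit 1 values. Code C4 automatically flags non-interruption at ≥5x ULN, whichever protocol text prevails. Code C5 describes signs of hepatic injury, or ≥3x ULN persisting despite at least two weeks of reduction or interruption. An isolated Visit 2 value of ≥3x to <5x meets neither description. No code removes a patient from an analysis set.

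**Conclusion.** The point holds as a minor safety clarification. For AST/ALT of ≥3x to <8x ULN at Visit 2 without signs of hepatic injury, 6.1 and Table 4.2.1.2:1 give different instructions and neither is given precedence. The practical risk is full-dose continuation for roughly two weeks in a patient whom the table would withdraw.

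The case should be rare, because it needs at least a doubling after a passing Visit 1 value. That is a judgement; no rate is given. The limit on exposure assumes that Visit 3 takes place on schedule and that its result is acted on.

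A reader might go further and infer that the protocol lets dosing continue through hepatic injury. It does not: 3.3.4.1 makes discontinuation mandatory there, including at ≥8x ULN. Nor is there any effect on endpoints, sample size or the planned analysis.

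**What to change.** Add one sentence to 6.1: for AST/ALT, continuation with written justification applies only to Visit 2 values of >1.5x to <3x ULN, and values of ≥3x ULN require withdrawal of trial medication under Table 4.2.1.2:1, with the patient still invited to attend visits. Optionally, add a cross-reference to the table beside the Visit 2 sentence in 3.3.3.

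This carries into 6.1 the ceiling the sponsor already set in the table. It leaves the rule for the other laboratory criteria as it is. The cost is one sentence, one optional cross-reference and a clarification to sites.
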